4.11 Secondary Outcomes

1) Clinical infection: as described above: 2) Culture confirmed bacterial infection (e.g., bacteremia, urinary tract infection, tonsillitis, abscess, osteomyelitis, meningitis) or PCR-confirmed infection with *Chlamydomphila pneumoniae* or *Mycoplasma pneumoniae* (from nasopharyngeal swab) in children with pneumonia/acute chest syndrome. Pneumonia (acute lower respiratory infection, ALRI) will be defined as: history of fever or measured axillary temperature $\geq 37.5^{\circ}\text{C}$, with age-specific tachypnea, cough, and an infiltrate and/or effusion on chest x-ray consistent with pneumonia (see Appendix II for full definition).

2) *Vaso-occlusive crises (VOC)*: pain with the requirement for oral morphine or IM diclofenac, per SCC guidelines.

3) *Change in height for age z-score*, from enrollment to 12 months follow up, calculated using WHO standards.

4) *Serious adverse events*: 1) death; 2) a life-threatening event; or 3) hospitalization > 7 days.

5) *Adverse events*: based on CTCAE criteria, with modifications for SCA, as in the NOHARM study, will be assessed at the 1, 3, 6, 9 and 12-month follow-up visits, and at all sick visits.

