2.0 SPECIFIC AIMS

The **specific aim** of the study is to determine if zinc supplementation reduces severe or invasive infections in Ugandan children 1.00-4.99 years of age with SCA.

The study will also assess **four secondary outcomes** that may be affected by zinc supplementation in children: 1) incidence of all clinically diagnosed infections; 2) incidence of culture or PCR-confirmed bacterial infections, 3) incidence of vaso-occlusive crises (VOC), and 4) change in height-for-age z-score. We hypothesize that children with SCA who receive zinc supplementation will have less clinical infections, less culture or PCR-confirmed bacterial infections, less VOC and better growth than children who receive placebo.

The primary study goal is assessment of severe or invasive infection, and the study is powered for that outcome. However, information on differences of confirmed bacterial infection, VOC, and growth will provide important preliminary data for future studies. Finally, the study will assess the **frequency of**

adverse events with zinc, with particular attention to nausea and vomiting, the most common side effects seen with zinc supplementation.

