A codebook with specific definitions for each infection, based on WHO or similar criteria, will be created, and clinicians will have to check off criteria for the infection in order to assign the diagnosis of that infection to the child. Children who have fever with no defined source or clinical syndrome consistent with a specific infectious organisms or clinical syndrome will have a diagnosis of “fever, no defined source”, and will not be included as “clinical infections” because fever could be non-infectious and because a “clinical infection” should conform to a clear clinical diagnosis or have PCR or culture confirmation of infection. Children with culture or PCR confirmed bacterial infections will be a subset of the children with clinical infections, and children with “fever, no source” as their initial diagnosis who are culture or PCR positive for an organism consistent with their clinical syndrome will have the diagnosis corrected to infection with the bacteria or virus confirmed by culture/PCR.

Culture or PCR-confirmed bacterial infections are a secondary objective in this aim. In many severe infections, including pneumonia, sepsis, osteomyelitis, sinusitis, and meningitis, blood cultures are often negative, and they are treated clinically. Other infections that are less severe in children with SCA, such as diarrhea, are typically viral in etiology, yet of clinical significance to these children and are known to be reduced with zinc supplementation. Malaria, which can cause severe disease in children with SCA is also not a bacterial infection. For these reasons, while we acknowledge that severe or invasive infection is a less specific outcome than proven bacterial infection (even with the rigorous definitions we will have in place for severe or invasive infection), we believe it is the right primary outcome for this aim.

For children with pneumonia/ALRI, the multiplex PCR test we use will determine, in addition to infection with *M. pneumoniae* and *C. pneumoniae*, infection with *B. pertussis*, and 17 viruses that commonly cause respiratory infections (see Testing Methods section below). This will provide additional epidemiologic information about viral infections causing febrile or URI syndromes in this population.

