6.2 Follow Up Clinical and Lab Assessments and Treatment for Acute Illness

Children in the study will have follow up visits at 1, 3, 6, 9 and 12 months. The visits will allow replenishment of zinc or placebo tablet supply, assess adherence (by pill counts), and evaluation of adverse events. They will also allow interim measurements of height and weight. Parents or guardians will be asked to bring their children to the NSCC for any illness. All care during the study will be provided without cost, and with reimbursement for transportation. A full list of study evaluations and testing is provided in the Study Evaluations SOP.

Children with illness will be evaluated clinically and all illnesses recorded on a sick visit case report form (CRF). Children will be managed according to the SCC treatment protocols developed at the Mulago

National Referral Hospital Sickle Cell Clinic. Definitions will be provided for the most common infections, which will be listed on the CRF, and any other infections will be entered as free text diagnosis. Children with pneumonia/acute lower respiratory tract infection (ALRI) will have a swab collected for later testing by nasopharyngeal swab PCR for *Mycoplasma pneumoniae*, *Chlamydomphila pneumoniae*, *Bordetella pertussis* and 17 viral upper respiratory infection (URI) pathogens. We are not able to do testing in real time, but treatment with a macrolide antibiotic is part of standard of care for children with pneumonia/ALRI. For this study children who have clinical signs of pneumonia (see Appendix I) will receive a chest x-ray to confirm the diagnosis of pneumonia. Other labs will be collected as needed for clinical diagnosis, and a blood sample collected and stored for future infectious pathogen or inflammatory response testing.

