6.4 Testing Methods

Plasma and urine zinc testing and plasma copper testing. At study completion, plasma zinc and copper levels and urine zinc levels will be tested in the baseline and 12 month samples at the Wright Lab at Mount Sinai Hospital, New York, New York or a similarly certified lab for zinc testing. Blood and urine samples will be collected using a tight trace metal specific sample collection protocol to minimize contamination.

Hemoglobin electrophoresis will be done using standard capillary electrophoresis techniques on fresh samples or thawed samples stored for <6 months.

PCR testing of NP swabs for C. pneumoniae, M. pneumoniae, B pertussis and 17 viral URI pathogens. Nasopharyngeal (NP) swab specimens will be analyzed using the FilmArray[®] Respiratory Panel (RP; BioFire Diagnostics, Salt Lake City, UT) by collaborators at the Indiana University Health Pathology Laboratory (IUHPL) in Indianapolis, IN.

Microscopy testing for malaria. Microscopy for *Plasmodium* species by thick and thin smear, with parasite quantification, will be performed as previously described²¹, with a minimum of two independent readings.

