Urinary tract infection	Symptoms (fever with urinary frequency, burning or new incontinence after prior toilet training) plus urinalysis positive for LE or nitrite OR clean catch urine culture with $>100,000$ colonies of a single pathogen

* Any child with a standard clinical diagnosis of pneumonia (clinical signs above) will be treated for pneumonia regardless of CXR findings, as this is Mulago Hospital Sickle Cell Clinic protocol. Chest x-rays will be read by on call radiologist for acute clinical care, and also saved for reading by second radiologist. Specific criteria will be assessed by both radiologists, and only children who meet criteria from the WHO Radiology Working Group for pneumonia will be given a final diagnosis of pneumonia (Cherian T et al, Bulletin of WHO, 2005;83:353-359). Children who do not meet radiographic criteria will be given a final diagnosis of “respiratory infection” and not included in primary category of “severe or invasive infections” that constitutes the primary study endpoint. They will be considered for the secondary endpoint of “all clinical infections”.

APPENDIX II. Common Terminology Criteria for Adverse Events (CTCAE) Version 4.0 and Exceptions to CTCAE

Table 1. Sickle Cell Disease Symptoms and Associated Conditions

Acute chest syndrome	Decreased lung function	Hypertension	Renal papillary necrosis
Adenotonsillar disease	Delayed growth/puberty	Hypocalcemia	Reticulocytopenia
Albuminuria	Depression	Hyposthenuria	Reticulocytosis
Amenorrhea	Dizziness	Nephropathy	Retinopathy
Anemia (severe)	Electrolyte imbalance	Osteomyelitis	Retinal hemorrhage
Aplastic crisis	Elevated urinary urobilinogen	Pain, back	Rhabdomyolysis
Arthralgia	Elevated serum transaminases	Pain, chest	Seizure
Avascular necrosis of hip/shoulder	Elevated TCD velocities	Pain, joint	Septicemia
Bacteremia	Fever	Pain, long bone	Silent organ infarction
Bone infarction	Empyema	Pain, severe abdominal	Skin ulcer
Cardiac arrhythmia	Hand-foot syndrome/dactylitis	Pain, sternal or rib	Splenic sequestration
Cardiomegaly	Headache	Priapism	Splenomegaly
Cerebrovascular accident	Hematuria	Proteinuria	Stroke
Cholecystitis	Hemiplegia	Pneumonia	Transient Ischemic Attack (TIA)
Cholelithiasis	Hemolysis	Pulmonary embolism	Transfusion, unanticipated
Cognitive dysfunction	Hepatic sequestration	Pulmonary hypertension	Vaso-occlusive pain
Constipation	Hepatomegaly	Pulmonary infiltrate on chest x-ray	
Cranial nerve palsy	Hospitalization >24 hours	Pyelonephritis	

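### The confirmed bacterial infection outcome omits B. pertussis, which its own swab panel tests for, and leaves out PCR positives in children reclassified on x-ray

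*Combined protocol and SAP*

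**What the plan says.** Section 2.0 lists among the secondary outcomes the "incidence of culture or PCR-confirmed bacterial infections", and section 9.2 plans its analysis under the same label. Neither limits the organism.

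Section 4.11 gives the operative definition. Any culture-confirmed bacterial infection counts, with examples. A PCR result counts only for C. pneumoniae or M. pneumoniae, and only "from nasopharyngeal swab) in children with pneumonia/acute chest syndrome". The same item defines pneumonia as fever, tachypnea and cough "and an infiltrate and/or effusion on chest x-ray consistent with pneumonia (see Appendix II for full definition").

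Section 6.2 says that children with pneumonia or acute lower respiratory infection "will have a swab collected for later testing by nasopharyngeal swab PCR for" M. pneumoniae, C. pneumoniae, B. pertussis and 17 viruses. Section 6.4 repeats the panel: "PCR testing of NP swabs for C. pneumoniae, M. pneumoniae, B pertussis and 17 viral URI pathogens".

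The Appendix I footnote describes an on-call x-ray reading for care and a reading by a second radiologist. Only children who meet the WHO radiographic criteria keep a final diagnosis of pneumonia. "Children who do not meet radiographic criteria will be given a final diagnosis of" respiratory infection. They leave the primary category and are considered for all clinical infections.

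**The concern.** The outcome's name and its definition do not match. Pertussis is a bacterial infection, and a positive PCR for it is a PCR-confirmed bacterial infection in the sense of sections 2.0 and 9.2. Under section 4.11 it is not an event. The plan gives no reason for the omission. Section 4.10 mentions B. pertussis on the panel, but the use it describes for the additional results is epidemiologic information on viruses, which does not cover a bacterium.

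The second gap appears only when section 4.11 is read with Appendix I. The child is swabbed because of a pneumonia or lower respiratory illness, but the diagnosis that decides whether the PCR result counts can change later. The plan does not say what happens to a positive result in a child whose diagnosis changes.

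Section 4.10 concedes that the primary outcome is less specific than proven bacterial infection. Readers will therefore look to this secondary outcome, and its case definition should be complete before anyone sees results by arm.

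**Working it through.** The plan gives no rate, power or expected count for this outcome, so there is no figure to reproduce. The check is a comparison of sections, followed by a rough size under stated assumptions.

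**1. Organisms**

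| Organism | On the panel (4.10, 6.2, 6.4) | Bacterium | Fits the label (2.0, 9.2) | Counted on PCR (4.11) |
|---|---|---|---|---|
| M. pneumoniae | yes | yes | yes | yes |
| C. pneumoniae | yes | yes | yes | yes |
| B. pertussis | yes | yes | yes | **no** |
| 17 viruses | yes | no | no | no |

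B. pertussis is the only row where label and definition disagree.

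**2. X-ray reclassification**

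- Section 4.11 counts a PCR positive only with pneumonia or acute chest syndrome, and its pneumonia definition needs an x-ray finding.
- Appendix I withdraws the pneumonia diagnosis when the final radiographic criteria are not met.
- Acute chest syndrome offers no other way in. Appendix I defines it as the pneumonia signs plus chest pain or tenderness.
- A PCR-positive child with a final diagnosis of respiratory infection is therefore outside the outcome.
- Section 4.11 refers to Appendix II for the full pneumonia definition, but that definition is in Appendix I. The text thus does not state cleanly that the final reading governs, although that is the natural reading.

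**3. Size, on assumed inputs**

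From the plan: 250 children and 10% loss to follow-up (section 9.1). Treating lost children as contributing no time gives 250 × 0.90 = 225 child-years over both arms.

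Assumed, because the documents give none of these:

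- 0.1 to 0.3 clinical pneumonia episodes per child-year, all swabbed
- 30% to 70% of these failing the final x-ray criteria
- 2% to 10% of swabs positive for M. or C. pneumoniae
- 1% to 5% of swabs positive for B. pertussis

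M. or C. pneumoniae positives in reclassified children = child-years × episode rate × share failing × positivity:

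- low: 225 × 0.1 × 0.30 × 0.02 = 0.14
- high: 225 × 0.3 × 0.70 × 0.10 = 4.73

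B. pertussis positives among all swabbed episodes = child-years × episode rate × positivity:

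- low: 225 × 0.1 × 0.01 = 0.23
- high: 225 × 0.3 × 0.05 = 3.38

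If 30% to 70% of the pertussis positives meet the final criteria, between 0.23 × 0.30 = 0.07 and 3.38 × 0.70 = 2.4 would enter the main outcome once pertussis is added. The rest would appear only in an analysis that ignores the x-ray reading.

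**The case against.** The strongest reply is that requiring radiographic pneumonia is a sensible specificity rule. A nasopharyngeal swab samples the upper airway, and the film ties a positive result to lower respiratory disease. Counting carriage as infection would dilute a rate ratio, so extra events are not simply extra precision. This stands, and it is why the main definition should keep the x-ray requirement. It does not explain the absence of B. pertussis, since a pertussis positive in a child with radiographic pneumonia meets the same requirement.

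Four stronger readings are tempting, and the documents do not support them.

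- A reader might infer that sections 4.10 and 4.11 give rival counts. Section 4.10 says "Children with culture or PCR confirmed bacterial infections will be a subset of the children with clinical infections". That is a containment statement: being a clinical infection is necessary, not sufficient. Every case under 4.11 satisfies it.
- A reader might infer that results already in hand are discarded. PCR is deferred, the order of swab and film is not fixed, and nothing says whether swabs from reclassified children will be run. Section 6.4 excludes none, but that is silence and not a commitment.
- A reader might infer that the rule in 4.10 for relabelling 'fever, no source' on a PCR result has no test behind it, because only pneumonia and lower respiratory illness are swabbed. Section 6.2 also stores illness-visit blood for later pathogen testing, so a PCR route may exist.
- A reader might infer a marked loss of precision. Losing 20%, 40% or 60% of events widens the standard error of a log rate ratio by 1/√0.8 = 1.12, 1/√0.6 = 1.29 or 1/√0.4 = 1.58. Those losses are assumed, and the factors apply only to the PCR component, for which no separate analysis is planned. Culture-confirmed events make the effect on the whole outcome smaller.

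**Conclusion.** The pertussis point holds on a direct reading: the definition leaves out a confirmed bacterial infection that the outcome's own label includes. The x-ray point holds as a gap left by section 4.11 and Appendix I together. It is not a contradiction, and it is no ground for dropping the radiographic requirement from the main definition.

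The size is unknown and probably small: about 0.2 to 3.4 pertussis episodes and 0.1 to 4.7 M. or C. pneumoniae episodes in total across both arms. These ranges rest entirely on the assumed episode, x-ray failure and positivity rates. The outcome is secondary, and section 2.0 presents confirmed bacterial infection as preliminary data for later studies. The primary outcome uses the Appendix I definitions and no swab PCR result, so it and its power are unaffected. The change is worth making because it is specific and nearly free.

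**What to change.** 1. In section 4.11, add B. pertussis to C. pneumoniae and M. pneumoniae as organisms whose PCR confirmation counts.
2. Keep pneumonia or acute chest syndrome by the final radiographic criteria as the main definition. Say so in section 4.11, and correct the reference from Appendix II to Appendix I.
3. In section 9.2, add one sensitivity analysis of this outcome, fixed before unblinding. It counts a PCR positive for any of the three bacteria in any child swabbed under section 6.2, whatever the final x-ray diagnosis. State that swabs from reclassified children will be tested.
4. Leave the 'fever, no source' wording in section 4.10 unchanged.

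The cost is protocol wording and one more model fit, since the swabs and the panel are already planned. The small downside is that some positives added by the sensitivity analysis may be carriage. Keeping them out of the main definition contains that risk.

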METHODS: The study will be a randomized, placebo-controlled, double blind clinical trial in which 250 Ugandan children 1.00-4.99 years of age with SCA will receive zinc (10 mg oral dispersible tablet daily) or placebo (identical to zinc in appearance) for 12 months. The primary study outcome will be incidence of severe or invasive infections. Secondary outcomes will include incidence of all clinical infections, confirmed bacterial infections (by culture or PCR), incidence of vaso-occlusive crisis (VOC), change in height-for-age z-score, and incidence of zinc-related adverse events.

IMPACT: If this trial shows a reduction in severe or invasive infection incidence, it would be the basis for a multi-site pre-post intervention clinical trial to assess real-world safety and efficacy of zinc in African children with SCA. Since zinc is safe, inexpensive, and easy to administer, this trial has the potential to improve the health of hundreds of thousands of African children with SCA through reduction of infection-related morbidity and mortality.

LIST OF ABBREVIATIONS

ZIPs = Zinc for Infection Prevention in Sickle cell anemia

Hb = Hemoglobin

HbF = Fetal hemoglobin

SCA = Sickle cell anemia

SCD = Sickle cell disease

WHO = World Health Organization

US FDA = United States Food and Drug Administration

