8.0 SAFETY ASSESSMENT AND REPORTING

8.1 Adverse Event Reporting Requirements

All adverse events (AE) and serious adverse events (SAE) will be collected and reported to the Medical and Data Coordinating Center at IU using the correct data collection forms. AE reporting will utilize the Common Terminology Criteria for Adverse Events (CTCAE) Version 4.0 available since 2009, where all AE are categorized by organ system and graded by severity. A list of expected and potentially serious AE's, as well as exceptions to the CTCAE's is included in Appendix II (Tables 1 and 2).

SAE reporting will use standard definitions (any life-threatening event hospitalization or death) however, since hospitalization is common in children with SCA, we will use hospital stay of more than 7 days to define hospitalization-related SAE in this study. This is based on the knowledge that children who are admitted with sickle cell-related conditions (such as anemia requiring transfusion, acute chest syndrome, and stroke) have an average length of stay of approximately 7 days. A SAE for this study will therefore be defined as: 1) hospitalization for more than 7 days; 2) any other life-threatening event* (based on clinician judgement); or 3) death. All SAEs will be followed until resolution or stabilization.

All SAEs will be reported via email to the in-country principal investigator or an assigned representative within 48 hours of the staff becoming aware of it, using an SAE form, which should be completed, scanned and sent electronically. The SAE form asks for nature of event, date of onset, severity, corrective therapies given, outcome and causality (i.e. unrelated, unlikely, possible, probably, definitely). The responsible study clinician should assign the causality of the event. Additional information will be sent within 14 additional days (full SAE report) if the condition has not resolved at the time of e-mail notification.

SAEs will be reported to the primary site IRB (Makerere University School of Medicine Research Ethics Committee) within 7 days of the team being aware of the SAE. Complied SAE logs will be sent to the Uganda National Drug Authority (NDA) in quarterly reports, and to the study IRBs and DSMB annually or as requested by those organizations.

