9.2 Proposed Analysis

We hypothesize that the incidence of infection in the zinc supplemented group will be $\geq 40\%$ lower than that of the placebo group. Incidence of clinical infection will be compared using Poisson or negative binomial regression analysis. Other factors that are potentially associated with the risk of infection will be included in the regression models as covariates. Analysis will be implemented using SAS PROC GENMOD or NLMIXED as appropriate. Similar analyses will be conducted for incidence of culture or PCR-confirmed bacterial infections, VOC, SAE and AE. Frequency of infection, culture or PCR-confirmed bacterial infection, VOC, AE and SAE will also be compared using χ^2 analyses.

We will conduct one interim analysis, for examination of the efficacy and futility of the trial. The interim analysis will be conducted at the time when we accumulate half of the expected outcome events. In the one-year follow-up period, we expect to see a total of 142 episodes of severe or invasive infections between the two trial arms. We plan to perform the interim analysis when we have 71 episodes of severe or invasive infections. We follow a symmetric two-sided group sequential design with 80% power and total 5% Type I error rate. Using the O'Brien-Fleming bounds, we determine the p values of spending function for the interim analysis to be 0.006. We will reject the null hypothesis when the p value of the interim analysis is less than 0.006.

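### The planned adverse-event comparison neither isolates nausea and vomiting nor separates scheduled from sick visits, so a benefit of zinc on illness can mask a tablet-related excess

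*Combined protocol and SAP*

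**What the plan says.** **Ascertainment.** Section 4.11 states that AEs "will be assessed at the 1, 3, 6, 9 and 12-month follow-up visits, and at all sick visits". Sections 4.10 and 6.2 ask caregivers to bring the child in for any illness, so illness determines how many sick visits there are.

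**Scope.** Section 8.1: "All adverse events (AE) and serious adverse events (SAE) will be collected and reported". It refers to Appendix II for expected and potentially serious AEs. Table 1 there includes fever, pneumonia, bacteremia, osteomyelitis and acute chest syndrome, several of which are also components of the primary endpoint in Appendix I.

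**Objective.** Section 2.0 sets out to assess the frequency of "adverse events with zinc, with particular attention to nausea and vomiting, the most common side effects seen with zinc supplementation". The abstract names the outcome more narrowly, as "incidence of zinc-related adverse events".

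**Analysis.** After describing Poisson or negative binomial regression for infections, section 9.2 says: "Similar analyses will be conducted for incidence of culture or PCR-confirmed bacterial infections, VOC, SAE and AE". It adds: "Frequency of infection, culture or PCR-confirmed bacterial infection, VOC, AE and SAE will also be compared using χ^2 analyses". It describes no analysis of nausea or vomiting, no split between scheduled and sick visits, and no separation of events that accompany an infection.

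**The concern.** The number of occasions on which an AE can be recorded is partly a consequence of the efficacy outcome. If zinc works, two things happen in the zinc arm. There are fewer sick visits, hence fewer assessments. There are also fewer illnesses, and so fewer illness events and symptoms, vomiting among them, that count as AEs. Both lower the zinc arm's AE rate whether or not the tablet is well tolerated.

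At stake is the safety aim. Section 5.2 names vomiting as the main side effect of zinc and calls it infrequent, so the signal is small and easily diluted. The abstract already argues from the safety of zinc to use in very large numbers of children. A null or favourable AE comparison, analysed as section 9.2 is written, could not tell good tolerability from prevented illness.

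**Working it through.** **1. The plan's own figures.** Inputs: placebo rate 0.71 severe or invasive infections per child-year and a 40% reduction (section 9.1); 125 children per arm (section 4.6); 142 expected episodes (section 9.2).

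- Zinc rate: 0.71 × 0.60 = 0.426.
- Expected episodes: 125 × (0.71 + 0.426) = 142.0, as stated.
- Power with 10% loss (112.5 per arm): the standard error of the log rate ratio is √(1/79.875 + 1/47.925) = 0.183. Then |ln 0.6|/0.183 − 1.96 ≈ 0.84, which gives 79.8% power, as stated.
- Severe infections avoided per child-year: 0.71 − 0.426 = 0.284.

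No stated figure is in dispute. The last line is what drives the difference in sick visits.

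**2. Assessments per child-year.** Assume five scheduled visits, S sick visits per placebo child-year (S = 1 to 4, not in the documents) and detection proportional to the number of visits. Two cases for the zinc-to-placebo ratio:

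- A, only the powered severe infections are avoided: (5 + S − 0.284)/(5 + S).
- B, every kind of sick visit falls by 40%: (5 + 0.6S)/(5 + S).

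| S | A | B |
|---|---|---|
| 1 | 5.716/6 = 0.953 | 5.6/6 = 0.933 |
| 2 | 6.716/7 = 0.959 | 6.2/7 = 0.886 |
| 3 | 7.716/8 = 0.965 | 6.8/8 = 0.850 |
| 4 | 8.716/9 = 0.968 | 7.4/9 = 0.822 |

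The inverse of each ratio is the true excess on zinc that would read as no difference: about 3% to 5% in case A and 7% to 22% in case B. The two cases move in opposite directions as S grows.

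**3. Illness symptoms counted as AEs.** This is illustration only, because none of these vomiting rates is in the documents. Assume 0.2 non-illness vomiting events per placebo child-year, a true ratio of 1.5 for these on zinc (0.3), and vomiting in a share v = 10% to 30% of illnesses. The observed vomiting ratio, lower v first, is then:

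- 0.71 illnesses per placebo child-year, cut to 0.426: 0.3426/0.271 = 1.26 to 0.4278/0.413 = 1.04.
- 2 illnesses, only 0.284 avoided: 0.4716/0.4 = 1.18 to 0.8148/0.8 = 1.02.
- 2 illnesses, all cut by 40%: 0.42/0.4 = 1.05 to 0.66/0.8 = 0.83.

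The direction is the same throughout. The size depends on the assumptions.

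**4. All AEs together.** If each severe infection counts as one AE, zinc would have to cause 0.284 extra AEs per child-year, about 0.284 × 125 = 35.5 in the arm, before the overall AE ratio reached 1.

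**The case against.** **The text does not say that all AEs go into one pooled comparison.** A reader might infer this from section 9.2, but that section lists SAEs separately and adds a chi-square comparison, section 8.1 categorises AEs by organ system and severity, and a by-event table is not ruled out. This stands. What remains is that no such table is prespecified. The abstract's narrower outcome does not close the gap: section 8.1 describes a causality rating only for serious events ("The SAE form asks for nature of event, date of onset, severity, corrective therapies given, outcome and causality"), and section 9.2 has no matching analysis.

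**The 40% is not a reduction in all sick visits.** A reader might take 0.93 to 0.82 as the expected dilution. The effect is powered for severe or invasive infections, while sick visits also arise from pain crises and from fever without a source, which section 4.10 does not count as a clinical infection. This stands; case B is an upper scenario.

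**Detection may not follow visit counts.** Section 6.2 has AEs evaluated at scheduled visits in both arms, and section 4.10 has caregivers asked there about outside clinic visits and the illnesses involved. If AEs are asked about in the same way, the ratio moves towards 1. This stands; the recall window for AEs is not stated.

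**Random error is larger than the ascertainment bias.** At the assumed 0.2 events per child-year there are about 25 per arm, and a 95% interval spans a factor of exp(1.96 × √(2/25)) ≈ 1.7 either way. This is fair for step 2. It does not remove a systematic shift, and step 3 can be larger.

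**Less vomiting because of fewer infections is a real benefit.** True: the all-visit comparison answers a valid question about total burden. It does not answer the tolerability question in section 2.0.

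**Restricting the main comparison to scheduled visits and excluding vomiting with an infection would create its own bias.** This also stands. It conditions on a post-randomisation event that zinc is meant to change, and it drops vomiting severe enough to prompt a visit. If events seen at sick visits were not re-entered at the next scheduled visit, more placebo events would be lost and a false zinc excess could appear.

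**Conclusion.** The concern holds in a limited form. As written, section 9.2 can confuse efficacy with tolerability, and it contains no analysis that answers the nausea and vomiting aim. The bias favours zinc and arises only if zinc reduces illness.

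Through ascertainment alone it is modest: a ratio of 0.95 to 0.97 if only the powered severe infections are avoided, and 0.93 to 0.82 under the stronger assumption that all sick visits fall by 40%. Both ranges rest on an assumed 1 to 4 sick visits per placebo child-year and on detection proportional to visits, and both move towards 1 with good recall at scheduled visits. Illness symptoms counted as AEs add bias of unknown size, possibly the larger part.

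A reader might infer that the plan will hide the side effects of zinc. The documents do not support that: five planned assessments are common to both arms, and a breakdown by event is not excluded. The supported statement is that a tablet-related excess can be masked and that the plan prespecifies nothing to reveal it. The primary efficacy analysis is not affected.

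**What to change.** Add to section 9.2:

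- Nausea and vomiting are each compared between arms as separate AE outcomes, using events from all visits.
- As a prespecified supporting analysis with equal planned ascertainment, the same comparison uses the month 1, 3, 6, 9 and 12 visits, counting events since the last scheduled visit whether or not they were already recorded at a sick visit.
- AEs are tabulated by arm and visit type (scheduled or sick). Those occurring with a diagnosed infection are shown separately, not excluded.

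Cost: SAP wording and one or two extra tables, with no change to visits, treatment or sample size. The scheduled-visit analysis will be less precise. The AE form is not in the documents, so someone must check that the forms record visit type, ask about events since the last scheduled visit, and allow an AE to be linked to a diagnosis.
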